Protocol Title: A Phase 1b Multi-cohort Study of the Combination of Pembrolizumab (MK-3475) plus Binimetinib alone or the Combination of Pembrolizumab plus Chemotherapy with or without Binimetinib in Participants with Metastatic Colorectal Cancer (KEYNOTE-651)	
Short Title: Ph1b study of MK-3475 with chemotherapy and/or binimetinib in participants with mCRC	
Objectives/Hypotheses and Endpoints: The objectives and endpoints apply to all participants enrolled in the trial. There is no intent to compare Cohorts B and C or Cohorts D and E. Each cohort will have independent objectives and will be analyzed separately.	
Primary	
Objective/Hypothesis	Endpoint
Objectives: 
To determine the safety and tolerability and to establish a preliminary recommended Phase 2 dose (RP2D) for the following cohorts:
Cohort A (pembrolizumab in combination with binimetinib in metastatic colorectal cancer (mCRC) participants previously treated with fluoropyrimidine, irinotecan, and oxaliplatin).Cohort B (pembrolizumab in combination with mFOLFOX7 in previously untreated mCRC participants).Cohort C (pembrolizumab in combination with mFOLFOX7 and binimetinib in previously untreated mCRC participants).Determined by incidence of dose limiting toxicities (DLTs)	

○ Cohort D (pembrolizumab in combination with FOLFIRI in mCRC participants previously treated with one line of a fluoropyrimidine plus oxaliplatin-based regimen).○ Cohort E (pembrolizumab in combination with FOLFIRI and binimetinib in mCRC participants previously treated with one line of fluoropyrimidine plus oxaliplatin-based regimen).	
---	--

Secondary

Objective:	Endpoint:

● To evaluate the objective response rate (ORR) based on Response Evaluation Criteria in Solid Tumors (RECIST) Version 1.1 as assessed by the investigator for each cohort.	
● Objective response rate (ORR): defined as the proportion of participants in the analysis population who experience complete response (CR) or partial response (PR) as assessed by the investigator based on RECIST Version 1.1.

Overall Design:

Trial Phase	Phase 1b
Clinical Indication	The treatment of participants with metastatic colorectal cancer (mCRC)
Population	Participants with mCRC with the non-microsatellite instability high/proficient mismatch repair (non-MSI-H/pMMR) phenotype
Trial Type	Interventional
Type of Design	Open label, multicenter, international, cohort-based, dose finding and dose confirmation Phase 1b
Type of Control	No treatment control
Trial Blinding	Unblinded Open-label

Estimated Duration of Trial	The Sponsor estimates that the trial will require approximately 48 months from the time the first participant signs the informed consent until the last participant's last study-related phone call or visit.
-----------------------------	---

Number of Participants:

A maximum of approximately 220 participants will be enrolled (Parts 1 and 2). A target sample size of 159 participants will be used for trial planning purposes.

Treatment Groups and Duration:

Treatment Groups	
This trial includes 2 parts: Part 1 will be a dose finding phase using the modified toxicity probability interval (mTPI) design and Part 2 will be a dose confirmation phase to further examine safety and exploratory efficacy. There are a total of 5 cohorts. Each of the 5 cohorts will participate in Part 1 and Part 2. The study will evaluate safety, tolerability, and efficacy in the following 5 cohorts:
 
Cohort A:
 
Part 1: Dose Finding
 
Standard dose (DL1): Pembrolizumab 200 mg intravenous (IV) every 3 weeks (Q3W) + binimatinib (oral) 30 mg twice daily (BID)
 
Escalation dose (DL2): Pembrolizumab 200 mg IV Q3W + binimatinib 45 mg (oral) BID
 
Part 2: Dose Confirmation
 
Pembrolizumab 200 mg IV Q3W + binimatinib (oral) (preliminary RP2D) BID
 
Cohort B:
 
Part 1: Dose Finding
 
DL1: Pembrolizumab 200 mg IV Q3W + mFOLFOX7 (oxaliplatin [85 mg/m²]; leucovorin [calcium folinate] [400 mg/m²]; fluorouracil [5-FU] 2400 mg/m² over 46 to 48 hours) IV every 2 weeks (Q2W).
 
De-escalation dose (DL-1): Pembrolizumab 200 mg IV Q3W + mFOLFOX7 (oxaliplatin [70 mg/m²]; leucovorin [calcium folinate] [400 mg/m²]; 5-FU [2000 mg/m² over 46 to 48 hours]) IV Q2W

------------------	--

Part 2: Dose Confirmation

Pembrolizumab 200 mg Q3W + mFOLFOX7 (preliminary RP2D) IV Q2W

Cohort C:

Part 1: Dose Finding

DL1: Pembrolizumab 200 mg IV Q3W + mFOLFOX7 (preliminary RP2D determined in Cohort B) IV Q2W + binimetinib 30 mg (oral) BID

DL2: Pembrolizumab 200 mg IV Q3W + mFOLFOX7 (preliminary RP2D determined in Cohort B) IV Q2W + binimetinib 45 mg (oral) BID

Part 2: Dose Confirmation

Pembrolizumab 200 mg IV Q3W + mFOLFOX7 (preliminary RP2D determined in Cohort B) IV Q2W + binimetinib (preliminary RP2D) (oral) BID

Cohort D:

Part 1: Dose Finding

DL1: Pembrolizumab 200 mg IV Q3W + FOLFIRI (irinotecan [180 mg/m²]; leucovorin [calcium folinate] [400 mg/m²]; 5-FU [2400 mg/m² over 46 to 48 hours]) IV Q2W

DL-1: Pembrolizumab 200 mg IV Q3W + FOLFIRI dose may be de-escalated (irinotecan [150 mg/m²]; leucovorin (calcium folinate) [400 mg/m²]; 5-FU 2000 mg/m² over 46 to 48 hours]) IV Q2W

Part 2: Dose Confirmation

Pembrolizumab 200 mg IV Q3W + FOLFIRI (preliminary RP2D) IV Q2W

Cohort E:

Part 1: Dose Finding

DL1: Pembrolizumab 200 mg IV Q3W + FOLFIRI (preliminary RP2D determined in Cohort D) IV Q2W + binimetinib 30 mg (oral) BID

DL2: Pembrolizumab 200 mg IV Q3W + FOLFIRI (preliminary RP2D determined in Cohort D) IV Q2W + binimetinib 45 mg (oral) BID

	
Part 2: Dose Confirmation
 
Pembrolizumab 200 mg IV Q3W + FOLFIRI (preliminary RP2D determined in Cohort D) IV Q2W + binimetinib (preliminary RP2D) (oral) BID

Duration of Participation	
Each participant will participate in the trial from the time the participant signs the informed consent form (ICF) through the final protocol-specified contact.
 
After a screening phase of 28 days, each participant will be assigned to receive study treatment until disease progression is radiographically documented and confirmed by the site per modified Response Evaluation Criteria in Solid Tumors 1.1, unacceptable adverse event(s) (AEs), intercurrent illness that prevents further administration of treatment, investigator's decision to withdraw the participant, noncompliance with study treatment or procedure requirements or administrative reasons requiring cessation of treatment, or until the participant has received 35 administrations of pembrolizumab (approximately 2 years) and binimetinib treatment. Treatment with standard of care (SOC) chemotherapy (mFOLFOX7 or FOLFIRI) will continue per Investigator's decision.
 
Once the participant has achieved the study objective or study has ended, the participant is discontinued from this study and may be enrolled in an extension study to continue protocol-defined assessments and treatment.

A list of abbreviations used in this document can be found in Appendix 1. Study governance considerations are outlined in Appendix 4.

2. Schedule of Activities (SoA)

2.1 Pembrolizumab in Combination with Binimetinib (Cohort A)

Trial Period:	Screening Phase		Treatment Cycles (3-Week Cycles)							End of Treatment	Post-treatment			Notes	
Treatment Cycle/Title:	Screening (Visit 1)		1	2	3	4	5	6	7	8 and beyond	Discon	Safety Follow-up	Follow-Up Visits	Survival Follow-up	
Scheduling Window (Days):	-42 to -29	-28 to -1	± 3	± 3	± 3	± 3	± 3	± 3	± 3	± 3	At time of discon	30 days post-discon	Q9W post-discon	Q12W	
Administrative Procedures															
Informed Consent		X													
Informed Consent for optional post-treatment tumor biopsy		X													
Informed Consent for FBR (optional)		X													
Participant Identification Card			X												
Inclusion/Exclusion Criteria			X												
Demographics and Medical History			X												
Cancer disease status and Prior Treatment history			X												
Prior and Concomitant Medication Review		X	X	X	X	X	X	X	X	X	X	X			
Pembrolizumab Administration			X	X	X	X	X	X	X	X					
Binimetinib Administration							X								To be administered BID.
Efficacy Assessments															
Tumor Imaging		X								X		X	X		Tumor imaging at screening must be performed within 28 days prior to the date of Cycle 1 Day 1. On-study imaging will be performed every 9 weeks (63 days \pm 7 days) calculated from the date of allocation. See section 9.2.

Pembrolizumab in Combination with Binimetinib (Cohort A)

Trial Period:	Screening Phase	Treatment Cycles (3-Week Cycles)								End of Treatment	Post-treatment			Notes	
		1	2	3	4	5	6	7	8 and beyond		Discon	Safety Follow-up	Follow-Up Visits	Survival Follow-up	
Treatment Cycle/Title:	Screening (Visit 1)									At time of discon	30 days post-discon	Q9W post-discon	Q12W		
Scheduling Window (Days):	-42 to -29	-28 to -1		±3	±3	±3	±3	±3	±3	±3	±3	±7	±7	±14	
Clinical Procedures/Assessments															
Review Adverse Events		X			X						X	X			
Full Physical Examination		X								X					
Full Ophthalmic Examination (Q8W)		X		X						X					To be performed at screening, Cycle 2 Day 1 and then every 8 weeks (±7 days) from Cycle 2 Day 1 and EOT. An ophthalmic examination at the 30-day follow up is only required if there was a clinically significant abnormality noted at EOT (± 7 days)
Directed Physical Examination			X	X	X	X	X	X	X						
Height, Weight, and Vital Signs		X	X	X	X	X	X	X	X	X					Height will be measured at Visit 1 only.
12-Lead Electrocardiogram		X		X	X	X	X	X	X	X	X	X			ECG will be performed in triplicate to confirm QTc interval at screening. ECG will be performed predose starting at Cycle 2.
Echocardiogram/MUGA scan (Q12W)		X		X			X			X	X				ECHO/MUGA scans are to be performed at Screening and pre-dose on Cycle 2 Day 1 and Cycle 5 Day 1, then every 12 weeks and EOT.
ECOG Performance Status		X	X	X	X	X	X	X	X	X					ECOG Performance Status at Screening to be assessed within 7 days prior to the first dose of trial treatment.

Pembrolizumab in Combination with Binimetinib (Cohort A)

Trial Period:	Screening Phase	Treatment Cycles (3-Week Cycles)							End of Treatment	Post-treatment			Notes
		1	2	3	4	5	6	7		Discon	Safety Follow-up	Follow-Up Visits	
Treatment Cycle/Title:	Screening (Visit 1)								At time of discon	30 days post-discon	Q9W post-discon	Q12W	
Scheduling Window (Days):	-42 to -29	-28 to -1		±3	±3	±3	±3	±3	±3	±3	±3	±7	±14
Post-study Anticancer Therapy Status												X	X
Survival Status			<=====X=====>									X	After investigator determined PD or start of new anticancer treatment. In addition, upon Sponsor request, participants may be contacted for survival status at any time during the course of the study.
LOCAL Laboratory Assessments													
MSI/MMR Status	X												If tumor testing is obtained by both PCR and IHC, the tumor result should be neither MSI-H by PCR nor dMMR by IHC to identify the non-MSI-H participants.
Pregnancy Test – Urine or Serum β -hCG, if applicable		X	X										Pregnancy tests may be performed if clinically warranted, or as defined by local regulations.
PT/INR and aPTT		X											
CBC with Differential ^a		X	X	X	X	X	X	X	X	X			
Chemistry Panel ^a		X	X	X	X	X	X	X	X	X			
Urinalysis ^a		X		X		X		X	X	X			To be performed at screening, and every other cycle starting at Cycle 2.
T3 or FT3, FT4, TSH		X		X	X	X	X	X	X	X			To be performed at screening, and every other cycle starting at Cycle 2.
Serum Tumor Marker			<=====X=====>									X	Serum tumor marker (CEA) to be collected Q3W starting at Cycle 1.
CENTRAL Laboratory Assessments													
Binimetinib Pharmacokinetics			X										PK samples will be collected at time 0 (pre-dose), 0.5, 1, 1.5, 2, 4, 6 hrs (all \pm 10 min) on Day 15, pre-dose (24 \pm 2 hrs from the first binimetinib PK collection) on Day 16 and pre-dose (48 \pm 2 hrs from the first binimetinib PK collection) on Day 17 in Cycle 1. The exact time of sample collection and time of administration of binimetinib will be recorded.
Blood for Genetic Analysis			X										To be collected pre-dose.

Pembrolizumab in Combination with Binimetinib (Cohort A)

Trial Period:	Screening Phase	Treatment Cycles (3-Week Cycles)							End of Treatment	Post-treatment			Notes	
		1	2	3	4	5	6	7		Discon	Safety Follow-up	Follow-Up Visits	Survival Follow-up	
Treatment Cycle/Title:	Screening (Visit 1)								At time of discon	30 days post-discon	Q9W post-discon	Q12W		
Scheduling Window (Days):	-42 to -29	-28 to -1		±3	±3	±3	±3	±3	±3	±3	±3	±7	±14	
Blood for RNA Analyses		X	X			X				X				Samples should be obtained pre-dose of Cycle 1, Cycle 2, and Cycle 5 and at the Treatment Discontinuation visit.
Blood for Plasma Biomarker Analyses		X	X			X				X				Samples should be obtained pre-dose of Cycle 1, Cycle 2, and Cycle 5 and at the Treatment Discontinuation visit.
Blood for Serum Biomarker Analyses		X	X			X				X				Samples should be obtained pre-dose of Cycle 1, Cycle 2, and Cycle 5 and at the Treatment Discontinuation visit.
Tumor Tissue Collection														
Archival or Newly Obtained Tumor Tissue collection	X													
On-Study Tumor Biopsy (Optional)			X											

Abbreviations: aPTT/PTT= activate; β-hCG=human chorionic gonadotropin; BID=twice daily; CBC=complete blood count; CEA= carcinoembryonic antigen; Discon=discontinuation; dMMR=deficient mismatch repair; ECG=electrocardiogram; ECHO=echocardiogram; ECOG=Eastern Cooperative Oncology Group; EOT=end of trial; FBR=future biomedical research; FT3=free triiodothyronine; FT4=free thyroxine; IHC= immunohistochemistry; IV=intravenous; MSI/MMR= microsatellite instability/mismatch repair; MUGA= multigated acquisition; PCR= polymerase chain reaction; PK= pharmacokinetic; PT/INR = prothrombin time/International Normalized Ratio; prothrombin time/partial thromboplastin time; Q8W=every 8 weeks; Q9W=every 9 weeks; Q12W= every 12 weeks; QTc =Q-T interval; RNA=ribonucleic acid; TSH=thyroid stimulating hormone.

a. All screening laboratory tests should be performed within 10 days prior to the first dose of trial treatment.

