7.2.1.2 Immune-Related Events and Dose Modification (Withhold, Treat, Discontinue)

Dose Modification and Toxicity Management for Immune-related AEs Associated with Pembrolizumab

AEs associated with pembrolizumab exposure may represent an immune-related response. These irAEs may occur shortly after the first dose or several months after the last dose of pembrolizumab treatment and may affect more than one body system simultaneously. Therefore, early recognition and initiation of treatment is critical to reduce complications. Based on existing clinical study data, most irAEs were reversible and could be managed with interruptions of pembrolizumab, administration of corticosteroids and/or other supportive care. For suspected irAEs, ensure adequate evaluation to confirm etiology or exclude other causes. Additional procedures or tests such as bronchoscopy, endoscopy, skin biopsy may be included as part of the evaluation. Based on the severity of irAEs, withhold or permanently discontinue pembrolizumab and administer corticosteroids.

Dose Modification and Toxicity Management Guidelines for irAEs associated with pembrolizumab monotherapy, coformulations, or IO combinations are provided in [Table 6](#).

See Section 7.7.1.4 for supportive care guidelines, including the use of corticosteroids.

Table 6 Dose Modification and Toxicity Management Guidelines for Immune-related Adverse Events Associated with Pembrolizumab Monotherapy, Coformulations or IO Combinations

General instructions:				
irAEs	Toxicity Grade (CTCAEv4.0)	Action With Pembrolizumab Monotherapy, Coformulations or IO Combinations	Corticosteroid and/or Other Therapies	Monitoring and Follow-up
Pneumonitis	Grade 2	Withhold	
 Administer corticosteroids (initial dose of 1-2 mg/kg prednisone or equivalent) followed by taper 	
 Monitor participants for signs and symptoms of pneumonitis Evaluate participants with suspected pneumonitis with radiographic imaging and initiate corticosteroid treatment Add prophylactic antibiotics for opportunistic infections
	Recurrent Grade 2 or Grade 3 or 4	Permanently discontinue		

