All AEs, SAEs and other reportable safety events that occur after the consent form is signed but before treatment allocation/randomization must be reported by the investigator if the participant is receiving placebo run-in or other run-in treatment, if the event cause the participant to be excluded from the trial, or is the result of a protocol-specified intervention, including but not limited to washout or discontinuation of usual therapy, diet, or a procedure.

- All AEs from the time of treatment allocation/randomization through 30 days following cessation of study treatment must be reported by the investigator.
- All AEs meeting serious criteria, from the time of treatment allocation/randomization through 90 days following cessation of study treatment, or 30 days following cessation of study treatment if the participant initiates new anticancer therapy, whichever is earlier must be reported by the investigator.
- All pregnancies and exposure during breastfeeding, from the time of treatment allocation/randomization through 120 days following cessation of study treatment, or 30 days following cessation of study treatment if the participant initiates new anticancer therapy must be reported by the investigator.

- Additionally, any SAE brought to the attention of an investigator at any time outside of the time period specified above must be reported immediately to the Sponsor if the event is considered to be drug-related.

Investigators are not obligated to actively seek AE or SAE or other reportable safety events in former study participants. However, if the investigator learns of any SAE, including a death, at any time after a participant has been discharged from the study, and he/she considers the event to be reasonably related to the study treatment or study participation, the investigator must promptly notify the sponsor.

All initial and follow-up AEs, SAEs and other reportable safety events will be recorded and reported to the sponsor or designee within the timeframes as indicated in [Table 10](#).

Table 10 Reporting Time Periods and Timeframes for Adverse Events and Other Reportable Safety Events

Type of Event	Reporting Time Period: Consent to Randomization/ Allocation	Reporting Time Period: Randomization/ Allocation through Protocol-Specified Follow-up Period	Reporting Time Period: After the Protocol Specified Follow-up Period	Timeframe to Report Event and Follow-up Information to SPONSOR:

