9.3.2 Method of Detecting AE, SAE and Other Reportable Safety Events

Care will be taken not to introduce bias when detecting AE and/or SAE and other reportable safety events. Open-ended and non-leading verbal questioning of the participant is the preferred method to inquire about AE occurrence.

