9.10.3.2 Safety Follow-up Visits

The mandatory Safety Follow-up Visit should be conducted approximately 30 days after the last dose of trial treatment or before the initiation of new anti-cancer treatment, whichever comes first. All AEs that occur prior to the Safety Follow-up Visit should be recorded. Participants with an AE of Grade >1 will be followed until the resolution of the AE to Grade 0-1 or until the beginning of a new anti-cancer therapy, whichever occurs first. SAEs that occur within 90 days of the end of treatment or before initiation of a new anti-cancer treatment should also be followed and recorded.

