9.10.3.5 Survival Follow-up Contacts

Participant survival follow-up status will be assessed approximately Q12W until death, withdrawal of consent, or the end of the study, whichever occurs first.

The first survival follow-up assessment should be scheduled as described below:

- For participants who discontinue treatment intervention and who will not enter the efficacy follow-up phase, the first survival follow-up contact will be scheduled 12 weeks after the discontinuation visit and/or safety follow-up visit (whichever is last).
- For participants who completed assessments in the efficacy follow-up phase, the first survival follow-up contact will be scheduled 12 weeks after the last efficacy assessment follow-up visit has been performed.

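### For participants who stop for progression and start no new therapy, no scheduled contact asks about SAEs between about Day 31 and Day 90 of the 90-day SAE reporting period

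*Combined protocol and SAP*

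**What the plan says.** Section 9.3.1 sets the SAE reporting period: "All AEs meeting serious criteria, from the time of treatment allocation/randomization through 90 days following cessation of study treatment", cut to "30 days following cessation of study treatment if the participant initiates new anticancer therapy, whichever is earlier". Section 9.10.3.2 repeats the duty for "SAEs that occur within 90 days of the end of treatment or before initiation of a new anti-cancer treatment". Section 9.3.2 says how events are to be found: "Open-ended and non-leading verbal questioning of the participant is the preferred method to inquire about AE occurrence".

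The contacts after treatment are these.

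- **Safety Follow-up.** About 30 days after the last dose (Section 9.10.3.2). The Cohort A schedule words it as "30 days post-discon". The window is ±7 days. If the post-trial visit comes early, Section 9.10.3.1 adds a telephone call at Day 30 to ask about adverse events.
- **Follow-up Visits every 9 weeks.** Only for participants who stop for a reason other than progression (Section 9.10.3.4).
- **Tumor imaging.** The discontinuation scan is the last one required after documented progression, unless the investigator applies iRECIST (Section 9.2.1.3).
- **Survival contacts every 12 weeks, ±14 days.** In the schedules they apply "After investigator determined PD or start of new anticancer treatment". For participants who do not enter efficacy follow-up, "the first survival follow-up contact will be scheduled 12 weeks after the discontinuation visit and/or safety follow-up visit", taking the later of the two visits (Section 9.10.3.5). Section 5.1.1.8 gives survival as the purpose of these contacts.

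On late toxicity, Section 7.2.1.2 states: "These irAEs may occur shortly after the first dose or several months after the last dose of pembrolizumab treatment".

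**The concern.** The plan sets a 90-day period for SAEs and prefers to find events by asking the participant. For one group it schedules no occasion on which to ask. That group is the participants who stop for progression and start no new therapy, so their 90-day period stays open.

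Participants in Cohorts B to E who stop for other reasons have an adverse-event review marked at the nine-weekly visits, as far as the tables can be read. The chance that an SAE after Day 30 is elicited therefore depends on why treatment ended. The Day 30 call in Section 9.10.3.1 shows that the plan does close the 30-day adverse-event period with a question. There is no counterpart for the 90-day SAE period.

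At stake is the completeness of late SAE data for new combinations whose overlapping toxicities the protocol itself lists (Section 3.3.1). SAEs are a summarized safety endpoint (Section 10.4.2). Safety data also inform dose decisions, because Section 5.1.1.1 looks at all the data before doses go forward to Part 2.

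**Working it through.** Days are counted from the last dose. The check is calendar arithmetic followed by a reading of the schedules. The plan gives no figure of its own to reproduce.

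1. **Inputs.** SAE period: Day 90 (Sections 9.3.1, 9.10.3.2). Safety Follow-up: Day 30 ±7, so Day 23 to 37 (Section 9.10.3.2 and the schedules). First survival contact: 12 × 7 = 84 days after that visit, ±14, so 70 to 98 days (Section 9.10.3.5 and the schedules).

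2. **Date of the first survival contact.**
   - Nominal: 30 + 84 = Day 114.
   - Earliest: 23 + 70 = Day 93.
   - Latest: 37 + 98 = Day 135.

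3. **Part of the SAE period with no scheduled question.**
   - Safety visit at Day 30: 90 − 30 = 60 days, and 60/90 = 67% of the period.
   - Safety visit at Day 37: 90 − 37 = 53 days.
   - Safety visit at Day 23: 90 − 23 = 67 days, or 60 again if the Day 30 call in Section 9.10.3.1 is made.

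4. **Comparison group.** A participant who stops without progression has the first nine-weekly visit at 63 ± 7 days, so Day 56 to 70 if counted from Day 0. In Cohorts B to E an adverse-event review appears to be marked there.

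5. **Does another anchor change the answer?** Section 5.1.1.8 counts the 12 weeks from confirmed progression. If that is Day 0, the contact falls at Day 84 (70 to 98). It is still a survival contact, so the question is still not scheduled.

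6. **Effect of adding the question.** A contact after Day 90 can ask about all of Days 31 to 90, so the unasked days fall from 60 to 0 for participants who are reached. What the date changes is recall. With a Day 30 safety visit, the contact under Section 9.10.3.5 falls between 30 + 70 = Day 100 and 30 + 98 = Day 128. Day 31 is then 69 to 97 days back (nominally 114 − 31 = 83). A contact at Day 90 to 104 makes that 59 to 73 days.

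**The case against.** The strongest reply is that the duty to report does not depend on a table mark. Section 9.3.1 makes SAE reporting mandatory through the period, and drug-related SAEs that come to the investigator's attention are reportable at any time. Section 9.10.3.2 tells sites to follow and record SAEs within 90 days and to follow adverse events above Grade 1. Section 8.1 asks for clinical-event data through the last scheduled follow-up. Deaths surface at the survival contacts. Some participants are seen anyway, through discretionary repeat imaging at 4 to 8 weeks (Table 9) or because their progression is not yet verified (Section 9.10.3.3). Nothing forbids a site from asking about SAEs on a survival call.

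This stands as a limit on the point. It would be too strong to say that late SAEs in this group go unrecorded. But these provisions act on events the site already knows of, or on contacts that are optional. The proactive follow-up in Section 9.3.3 begins only after a first report, and the extra contacts the sponsor may request are for survival status. None of them schedules the question.

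A reader might also infer that the defect is the timing, since the survival contact falls after Day 90. The documents do not support that. The period is defined by when an SAE occurs, not when it is found, so a later contact can cover all of it. A reader might add that the start of new therapy is never asked. In fact post-study therapy status already appears on the survival contact.

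**Conclusion.** The point holds as a gap in scheduled ascertainment. For participants who stop for progression and start no new therapy, no scheduled contact asks about SAEs over about 60 of the 90 reportable days (53 to 67 with the visit window). It merits a protocol change because the change is small and the gap is tied to the reason for stopping.

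It rests on two readings: that the first survival contact follows Section 9.10.3.5, and that no adverse-event review is marked in the Survival Follow-up column. The second should be confirmed in the formatted tables. Participants who start new therapy are outside the point, because Section 9.3.1 then closes the period at 30 days.

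Three stronger conclusions are not supported.

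- **The primary endpoint is not affected.** Dose-limiting toxicity is counted over the first 21 or 28 days of treatment. Late SAEs could bear on dose selection only through the wider review of all the data.
- **No share of participants affected can be given.** The documents state neither how many will stop for progression nor how many will start new therapy by Day 90.
- **Nothing can be concluded about adverse-event review at the Cohort A Follow-up Visits.** The column alignment in that table is too damaged in the available text.

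**What to change.** In the first bullet of Section 9.10.3.5 and in the Survival Follow-up column of all five schedules (Sections 2.1 to 2.5), mark an adverse-event review on the first survival contact. Limit it to SAEs up to 90 days after the last dose or the start of new anticancer therapy, with a cross-reference to Section 9.3.1. Preferably, time that first contact at Day 90 (+14 days) after the last dose to shorten recall, and continue every 12 weeks from there. If the timing is left as it is, the added question alone closes the gap.

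The cost is protocol wording, one table mark per cohort and a few more questions on a call already planned. No visit or procedure is added. Reported SAE counts may rise slightly because late events are better ascertained.
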